APPENDIX 2 LABORATORY ASSESSMENTS

The following safety laboratory parameters will be measured by the central laboratory:

Hematology	Serum Chemistry	Urinalysis^a
CBC, including differential count	• Sodium	• Specific gravity
	• Potassium	• pH
Platelet count	• Chloride	• Protein
	• Bicarbonate	• Glucose
	• Calcium	• Leukocyte esterase
	• Magnesium	• Blood
	• BUN	
	• Creatinine	
	• ALP	
	• ALT	
	• AST	
	• Total bilirubin	
	• CPK ^b	
	• Glucose	
	• Protein	
	• Albumin	

ALT, alanine aminotransferase; ALP, alkaline phosphatase; AST, aspartate aminotransferase; BUN, blood urea nitrogen; CBC, complete blood count; CPK, creatine phosphokinase.

^w Urine microscopy will be performed if there is a significant abnormality in the dipstick.

^x If CPK is high, troponin I will be performed and reported.

At the investigator's discretion, safety laboratory assessments may be repeated on Day -1 to confirm study eligibility before dosing of study medication.

The following non-safety laboratory parameters will be measured at Screening:

- Hepatitis panel (HVB and HVC)
- HIV test
- FSH
- TSH
- Testing for alcohol and drugs of abuse

APPENDIX 3 POTENTIAL DRUG-INDUCED LIVER INJURY REPORTING AND ADDITIONAL ASSESSMENTS REPORTING

To facilitate appropriate monitoring for signals of DILI, cases of concurrent aspartate AST/ALT and TBL elevation according to the criteria specified in [Section 7.4](#) ($3 \times$ ULN for AST/ALT and $2 \times$ ULN for TBL in subjects with no underlying liver disease and eligibility criteria requiring normal liver function at baseline) require the following:

- The event is to be reported to MyoKardia as an SAE within 24 hours of discovery or notification of the event (i.e., before additional etiologic investigations have been concluded).
- The appropriate case report form (CRF) (e.g., Adverse Event CRF) that captures information necessary to facilitate the evaluation of treatment-emergent liver abnormalities are to be completed and sent to MyoKardia.

Other events of hepatotoxicity and potential DILI are to be reported as SAEs if they meet the criteria for an SAE defined in [Section 10.1.2](#).

Additional Clinical Assessments and Observation

All subjects in whom investigational product(s) or protocol-required therapies is/are withheld (either permanently or conditionally) due to potential DILI or who experience AST/ALT elevations $> 3 \times \text{ULN}$ are to undergo a period of “close observation” until abnormalities return to normal or to the subject’s baseline levels. Assessments that are to be performed during this period include the following:

- Repeat liver chemistries within 24-48 hours (ALT, AST, ALP, TBL); in cases of TBL $> 2 \times \text{ULN}$ or AST/ALT much greater than $3 \times \text{ULN}$, retesting is to be performed within 24 hours.
 - Subjects are to be monitored at least twice weekly; testing frequency may decrease to once per week or less if laboratory abnormalities stabilize or the investigational product(s) or protocol-required therapies have been discontinued AND the subject is asymptomatic.
- Obtain prothrombin time/international normalized ratio, fractionated bilirubin, and any other potentially relevant laboratory evaluations of liver function or disease.
- Obtain complete blood count with differential to assess for eosinophilia.
- Obtain appropriate blood sampling for PK analysis if this has not already been collected.
- Obtain a more detailed history of the following:
 - prior and/or concurrent diseases or illness
 - exposure to environmental and/or industrial chemical agents
 - symptoms (if applicable) including right upper quadrant pain, hypersensitivity-type reactions, fatigue, nausea, vomiting, and fever
 - prior and/or concurrent use of alcohol, recreational drugs, and special diets
 - concomitant medications (including nonprescription medicines and herbal and dietary supplements)
- Initiate full viral and autoimmune hepatitis evaluation (serologies for hepatitis A, B, C, D, E, Epstein-Barr virus, herpes simplex virus, etc.); evaluate for other potential causes of

DILI, including but not limited to: NASH, hypoxic/ischemic hepatopathy, and biliary tract disease.

- Obtain gastroenterology or hepatology consult.
- Perform appropriate liver imaging or biopsy if clinically indicated; strongly consider these tests in cases of concurrent transaminase and TBL elevation as specified in [Section 7.4](#).
- Follow the subject until all laboratory abnormalities return to baseline or normal. The “close observation period” is to continue for a minimum of 4 weeks after investigational product(s) or protocol-required therapies discontinuation.

The potential DILI event and additional information such as medical history, concomitant medications and laboratory results must be captured in corresponding CRFs.

9.5.	ELECTROCARDIOGRAM.....	17
10.	PHARMACOKINETICS.....	18
11.	PK-QTC ANALYSES.....	18
12.	PHARMACOGENOMIC/HCM GENOTYPE	19
13.	INTERIM ANALYSIS	19
14.	CHANGES IN THE PLANNED ANALYSIS	19
14.1.1.	References.....	20
APPENDICES.....		21

List of Abbreviations

2D	2-dimensional
3D	3-dimensional
AE	adverse event
ALP	alkaline phosphatase
ALT	alanine aminotransferase
AST	aspartate aminotransferase
BLQ	Below the limit of quantitation
BMI	body mass index
BP	blood pressure
CPET	cardiopulmonary exercise testing
CRF	case report form
CV	coefficient of variation
DILI	drug-induced liver injury
DNA	deoxyribonucleic acid
ECHO	echocardiogram
EOS	End of Study
ECG	Electrocardiogram
HCM	hypertrophic cardiomyopathy
HR	heart rate
HSE	Hemodynamic stress echocardiography
IB	Investigator's Brochure
ICH	International Council for Harmonisation
IMP	investigational medicinal product
KCCQ	Kansas City Cardiomyopathy Questionnaire
LME	linear mixed effects
LS	least squares
LVEF	left ventricular ejection fraction
LVFS	left ventricular fractional shortening
LVOT	left ventricular outflow tract
MedDRA	Medical Dictionary for Regulatory Activities
MMRM	mixed effect model with repeated measures
NRS	numeric rating scale
NT-proBNP	N-terminal pro B-type natriuretic peptide
NYHA	New York Heart Association
OSS	overall summary score
PD	pharmacodynamic(s)
PK	pharmacokinetic(s)
PT	preferred term
pVO ₂	peak oxygen uptake

QTc	corrected QT interval
QTcB	QTc Bazett
QTcF	QTc Fridericia
RR	respiratory rate
SAE	serious adverse event
SE	standard error
SD	standard deviation
SOC	system organ class
TBL	total bilirubin
TEAE	treatment-emergent adverse event
TTE	transthoracic echocardiography, transthoracic echocardiogram
VCO2	carbon dioxide production
VE	volume expired
WHO	World Health Organization

1. Introduction

Hypertrophic cardiomyopathy (HCM), an autosomal dominant genetic disease, is defined clinically as unexplained left ventricular (LV) hypertrophy in the absence of known causes such as pressure overload, systemic diseases, or infiltrative processes (Gersh et al., 2011). The phenotypic hallmark of HCM is myocardial hypercontractility accompanied by reduced LV compliance, reflected clinically as reduced ventricular chamber size, often supranormal ejection fraction, and diastolic dysfunction. Mutations in cardiac myosin and other sarcomere proteins in patients with HCM appear to increase net power generation by the sarcomere (Chuan et al., 2012; Sommese et al., 2013; Sung et al., 2012), which is consistent with the generally hypercontractile state and impaired compliance of the myocardium observed clinically in patients with HCM.

MYK-461 is a first-in-class small molecule allosteric modulator of striated muscle myosin that selectively targets cardiac myosin and reversibly inhibits its binding to actin. MYK-461's profile of myosin modulation is predicted to reduce dynamic left ventricular outflow tract (LVOT) obstruction in patients with obstructive HCM by reducing systolic hypercontractility and dynamic obstruction in the near term, and reducing ventricular hypertrophy with chronic treatment. MyoKardia is developing MYK-461 for the treatment of adults with symptomatic obstructive HCM to relieve obstruction, improve symptoms, and increase exercise capacity.

In nonclinical studies, MYK-461 was specific for striated muscle myosin and selective for the cardiac isoform (see the MYK-461 Investigator's Brochure [IB]). Its targeted mechanism of action and high degree of specificity were reflected in its pharmacology in vitro and in vivo, as well as in the toxicology and safety pharmacology. In a feline model of HCM with LVOT obstruction, treatment with MYK-461 reduced contractility and relieved obstruction in an exposure-dependent manner (Stern et al., under review). The totality of the pharmacodynamic (PD) and tolerability data observed to date can be interpreted as direct or indirect consequences of altered cardiac contractility.

Please refer to the IB for more detailed information on MYK-461.

2. Objectives

2.1. Primary Objective

The primary objective of this study is:

- To characterize the effect of 12 weeks of MYK-461 treatment on reducing post-exercise peak LVOT gradient in subjects with symptomatic HCM and LVOT obstruction.

2.2. Secondary Objectives

The secondary objectives of this study are:

- To assess the proportion of subjects achieving an LVOT gradient response of post-exercise peak gradient < 30 mm Hg
- To assess the effects of 12 weeks of MYK-461 treatment on dyspnea symptom score, peak oxygen uptake (pVO₂), and volume expired (VE)/carbon dioxide production (VCO₂) slope
- To evaluate the pharmacokinetic (PK) of MYK-461
- To evaluate the PD of MYK-461 as assessed by a variety of echocardiographic imaging parameters
- To evaluate the safety and tolerability of MYK-461
- To evaluate the posttreatment reversibility of the effects of MYK-461 after 4 weeks of washout

in subjects with symptomatic HCM and LVOT obstruction.

2.3. Exploratory Objectives

The exploratory objectives of this study are:

- To assess the proportion of subjects achieving an LVOT gradient response of post-exercise peak gradient < 10 mm Hg
- To assess the effects of 12 weeks of MYK-461 treatment on New York Heart Association (NYHA) functional class, N-terminal pro B-type natriuretic peptide (NT-proBNP), and the Kansas City Cardiomyopathy Questionnaire (KCCQ) Overall Summary Score (OSS)
- To assess the effects of MYK-461 treatment on arterial pulse wave morphology assessed using an optical biosensor
- To assess the effect of MYK-461 treatment on heart rate (HR) and heart rhythm as assessed using a cardiac monitoring skin patch

[figure not shown]
in subjects with symptomatic HCM and LVOT obstruction.

3. Investigational Plan

3.1. Overall Study Design and Plan

This is a non-randomized, phase 2 open-label pilot study to evaluate the efficacy, PK, PD, safety, and tolerability of MYK-461 in subjects with symptomatic HCM and LVOT obstruction. Approximately 20 adult subjects with symptomatic HCM, a resting LVOT gradient ≥ 30 mm Hg, and post-exercise peak LVOT gradient ≥ 50 mm Hg will be enrolled. Approximately 10 subjects will participate in Part A and approximately 10 subjects will participate in Part B. The study will have a 12-week treatment phase and a 4-week washout phase (Figure 1).

Figure 1 Study Schema

CPET, cardiopulmonary exercise training; D, day; HSE, hemodynamic stress echocardiography; N, number PK, pharmacokinetic sample; RE/V, resting echocardiography/Valsalva; W, week

At Screening, subjects will undergo transthoracic echocardiography (TTE) in the supine or left lateral decubitus position. In addition to a standardized complete TTE, both resting instantaneous peak LVOT gradient (baseline) and provoked peak LVOT gradient (Valsalva maneuver) will be collected. Subjects will then undergo a standard symptom-limited exercise test (hemodynamic stress echocardiography). Subjects will be assessed systematically for symptoms of dyspnea and/or angina. Instantaneous peak LVOT gradient will be assessed immediately post-exercise by TTE.

On Day 1, resting TTE will be performed, blood samples will be drawn for PK, and subjects will have an assessment of pVO₂, VE/VCO₂, and other variables via cardiopulmonary exercise testing (CPET). After CPET, subjects will be dosed with open-label oral MYK-461 at the investigational site and will be observed for at least 1 hour after dosing, with assessment of vital signs and electrocardiograms (ECGs) at 1 hour postdose. Subjects will then be supplied with MYK-461 sufficient for once daily (QD) dosing at home.

Subjects will be evaluated at the investigational site at Weeks 1, 2, 3, 4, 5, 6, 7, 8, 12, and 16. At each of these visits, resting TTE will be performed and blood samples will be drawn for PK. On study visit days, study medication will be administered at the investigational site in order to collect blood samples for PK ≤ 2 hours prior to dosing. At Weeks 4, 12, and 16, hemodynamic stress echocardiography will be performed and peak LVOT gradient will be assessed. CPET will be conducted between Weeks 10 and 12 (inclusive).

Part A:

The MYK-461 starting dose will be 10 mg for subjects who weigh ≤ 60 kg and 15 mg for subjects who weigh > 60 kg. At the end of Week 4 (Day 28), each subject's left ventricular ejection fraction (LVEF) will be evaluated, and the subject's dose may be increased, decreased, or remain unchanged based on the predetermined criteria in Table 1, in consultation between the investigator and the medical monitor. If MYK-461 plasma concentration exceeds 750 ng/mL at Week 2, no dose increase is allowed, regardless of LVEF data at Week 4; however, dose decrease per LVEF data is allowed in this circumstance. The subject will subsequently receive that dose from Week 5 through Week 12.

Table 1 Part A Week 4 Dose Adjustment Criteria

Percent Decrease From Baseline in LVEF at the End of Week 4 (Day 28)	Action for MYK-461 Dose Week 5-Week 12 ^a
< 10	increase dose by 10 mg
≥ 10 and < 15	increase dose by 5 mg
≥ 15 and < 20	no change in dose
≥ 20	decrease dose by 5 mg

LVEF, left ventricular ejection fraction

^a No dose increase allowed if plasma concentration of MYK-461 > 750 ng/mL at Week 2.

Part B:

The MYK-461 starting dose will be 2 mg. At the end of Week 4 (Day 28), each subject's resting (non-provoked) peak instantaneous LVOT gradient and LVEF from the Week 4 TTE will be evaluated. The subject's dose will be increased to 5 mg or remain unchanged based on the predetermined criteria in Table 2 below, in consultation between the investigator and the medical monitor. If MYK-461 plasma concentration exceeds 300 ng/mL at Week 2, no dose increase is allowed. The subject will subsequently receive that dose from Week 5 (Day 29) through Week 12.

For all subjects who provide consent, blood will be drawn prior to dosing on Day 1 for assessment of HCM genotype and potentially additional deoxyribonucleic acid (DNA) sequencing.

In addition, subjects may consent separately to collection of pharmacogenetic samples that will be stored for potential future analysis of genetic biomarkers of efficacy, safety-related, PD, or PK parameters as determined by future studies using clinically meaningful endpoints, through DNA sequencing or other genetic testing.

Blood samples will be collected from all subjects prior to dosing on Day 1 and at Week 12 and stored for exploratory circulating biomarker analysis, e.g., proteomic analysis related to disease activity, metabolic pathways, efficacy measures, or safety measures.

The expected study duration is approximately 8 months (4 months for recruitment and 4 months for study conduct) for Part A and approximately 10 months for Part B (18 months in total). Each subject is expected to be in the study no more than 140 days: up to 28 days for screening and up to 112 days for study conduct.

Table 2: Part B Week 4 Dose Adjustment Criteria

Percent Decrease From Day 1 in Resting TTE Instantaneous Peak LVOT gradient at the End of Week 4 (Day 28)	Action for MYK-461 Dose Week 5-Week 12 ^a
< 50%	increase dose to 5 mg
≥ 50%	no change in dose

^a LVOT, left ventricular outflow tract; TTE, transthoracic echocardiogram; No dose increase allowed if plasma concentration of MYK-461 > 300 ng/mL at Week 2.

3.2. Study Endpoints

3.2.1 Primary Endpoint

- Change in post-exercise peak LVOT gradient from baseline to Week 12

3.2.2 Secondary Endpoints

- Proportion of subjects achieving an LVOT gradient response of post-exercise peak gradient < 30 mm Hg
- Change in dyspnea symptom score from baseline to Week 12
- Change in pVO₂ and VE/VCO₂ from baseline to Week 12
- Change from baseline in LVEF 2-dimensional (2D) and 3-dimensional (3D), global longitudinal strain, and left ventricular fractional shortening (LVFS) from baseline to Week 12
- Change from Week 12 to Week 16 in post-exercise peak LVOT gradient
- Plasma PK profile of MYK-461 treatment

3.2.3 Exploratory Endpoints

- Proportion of subjects achieving an LVOT gradient response of post-exercise peak gradient < 10 mm Hg
- Change in NYHA functional classification from baseline to Week 12
- Change in NT-proBNP from baseline to Week 12
- Change in KCCQ OSS from baseline to Week 12
- Change from baseline in arterial pulse wave morphology assessed using an optical biosensor
- Change from baseline in HR and heart rhythm assessed using a cardiac monitoring skin patch

3.2.4 Safety Endpoints

- Treatment-emergent adverse events (TEAEs) and serious adverse events (SAEs)
- Changes from baseline in laboratory values and vital signs

- Changes from baseline in ECGs

3.3. Treatments

All subjects will receive MYK-461 in an open-label manner.

Investigational medicinal product (IMP) is defined as MYK-461. Study medication is used throughout this protocol to refer to IMP as well as any other protocol-required medications (note that for this protocol there are no other required study medications).

3.4. Dose Adjustment/Modifications

All subjects in Part A will be assigned to a starting dose of oral MYK-461 based on body weight for doses ≥ 10 mg, which they will receive QD for 4 weeks. Subjects in Part B will be assigned a starting dose of 2 mg. At the Week 4 visit, dose adjustment may be performed based on the predetermined criteria in Section 3.1, Table 1 (Part A) and Table 2 (Part B). The subject will subsequently receive that dose from Week 5 (Day 29) through Week 12.

Subjects with abnormal hepatic laboratory values (e.g., alkaline phosphatase [ALP], aspartate aminotransferase [AST], alanine aminotransferase [ALT], total bilirubin [TBL], or international normalized ratio) or signs/symptoms of hepatitis may meet the criteria for withholding of study medication or other protocol-required therapies. Withholding is either permanent or conditional depending on the clinical circumstances discussed in the protocol.

4. General Statistical Considerations

All statistical analyses and programming of tables, figures, and listings will be performed by PPD using the SAS® Version 9.2 or higher (SAS Institute Inc., Cary, North Carolina, USA).

Unless otherwise specified, all tables will be presented with the columns labeled with the combination of 'initial dose'/'adjusted dose'.

Descriptive summaries will consist of the number and percentage of subjects in each category for discrete variables, and the sample size, mean, median, standard deviation (STDEV), first and third quartiles, minimum and maximum for continuous variables. For the analysis of primary endpoint using a mixed-effect model with repeated measures (MMRM), LS mean with standard error (SE) will also be provided. Standard error formatting should be presented to 4 more decimal places than the measured value.

P-values will be rounded to 4 decimal places. P-values that round to 0.0000 will be presented as '< 0.0001' and p-values that round to 1.000 will be presented as '> 0.9999'. Confidence intervals (CIs) will be estimated based on the MMRM for the analysis of the primary endpoint, a two-sided 90% significance level.

All mean and quartile values will be formatted to one more decimal place than the measured value. Standard deviation values will be formatted to 2 more decimal places than the measured value. All percentages will be rounded to 1 decimal point. The number and percentage of responses will be presented in the form XX (XX.X), where the percentage is in the parentheses.

All analysis and summary tables will have the analysis population sample size (i.e., number of subjects) in the column heading. All listings will be sorted for presentation in order of study site, subject identification and date of procedure or event.

The day of the first dose of study drug will be defined as Day 1.

Baseline value will be defined as the last non-missing value in date/time before the first dose of study drug is administered.

Missing data handling will be described in Section 7, 8, 9 and 10.

All laboratory data will be reported using International System of Units (SI).

The planned analysis visit window for weekly visits will consider +/- 3 days of the scheduled visit date based on the date of first exposure to the study drug. For a missed visit, the evaluation will be rescheduled as close as possible to the original planned visit, thus analysis windows have been designed to be all-inclusive. If more than one result is available for a particular visit window and results are equidistant from the analysis target date, the later result will be selected to break the tie. The associated visit window with corresponding visit is tabulated below.

Visit	Scheduled Visit Day	Visit Window
Day 1	Day 1	[1, 4]
Week 1	Day 8	[5, 11]
Week 2	Day 15	[12, 18]
Week 3	Day 22	[19, 25]
Week 4	Day 29	[26, 32]
Week 5	Day 36	[33, 39]
Week 6	Day 43	[40, 46]
Week 7	Day 50	[47, 53]
Week 8	Day 57	[54, 64]
Week 10*	Day 71	[65, 78]
Week 12*	Day 85	[79, 99]
Week 16	Day 113	[100, 116]

*CPET may be conducted between study visits 10 and 12, therefore the planned analysis window ranges from Day 65 to Day 99 with Day 85 set to the scheduled visit day. Note: The window is adjusted for visit 12; visit 10 will not be presented.

For any subjects who discontinued treatment prior to Week 4 dose adjustment, the subjects will not be presented in the treatment columns (initial dose/adjusted dose), however will be presented in the total column in the table.

If the “seconds” portion of the date/time variable is missing or not collected, it will be imputed as “:00”, as needed.

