5.5 Withdrawal and Replacement of Subjects

5.5.1 *Withdrawal from the Study*

Study participants may withdraw from further participation in the study at any time and for any reason. The degree to which a study participant withdraws can vary, and efforts will be made to collect important safety data if feasible and the study participant agrees. Study participants can:

- Withdraw from treatment and agree to participate in the Early Termination and End of Study (EOS) visits
- Withdraw from treatment and agree to participate in the Early Termination visit
- Withdraw from treatment and all follow-up

The investigator or MyoKardia may withdraw a study participant from treatment in the study for any of the following (or other) reasons:

- AE
- Noncompliance with study procedures/restrictions
- Study termination by MyoKardia

In all cases, the reason(s) for study withdrawal will be recorded in the source document and on the appropriate electronic case report form (eCRF).

5.5.2 *Replacement of Subjects*

Subjects who do not receive MYK-461 may be replaced. Subjects who drop out of the study for reasons other than AEs after receiving study medication may be replaced at the discretion of MyoKardia.

All data from subjects who receive at least 1 dose of IMP will be documented and maintained in the clinical trial database.

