4.3.2. Efficacy Analysis Population

The Efficacy Analysis Population is defined as all subjects who receive at least 1 dose of MYK-461 and have primary or secondary endpoint data, including a baseline value and at least one post baseline value. All efficacy analyses will be performed on the Efficacy Analysis Population. Subjects in the efficacy population will be analyzed according to the planned dose combination.

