8.1. Primary Efficacy Endpoint

The primary efficacy endpoint is the change from baseline to Week 12 in post-exercise peak LVOT gradient. Baseline is defined as the last non-missing measurement of post-exercise LVOT gradient prior to the first dose. Post-exercise peak LVOT gradient will be analyzed using a mixed-effect model with repeated measures (MMRM). All data available from baseline (Screening) to Week 16 (EOS) will be included and missing data will be accounted for by the MMRM model. The model will include the fixed categorical effects of timepoint: baseline, Week 4, Week 12 (end of treatment), and Week 16 (EOS). An unstructured covariance structure will be assumed unless model diagnostics suggest otherwise.

This model will provide least-squares (LS) mean estimates with their corresponding standard errors at each time point. Comparison between baseline and Week 12 (end of treatment) will be based on the LS mean difference obtained from the MMRM, and will be presented with its associated two-sided 90% confidence interval. Statistical significance of the difference versus baseline will be evaluated at the two-sided 0.10 level. The primary efficacy endpoint will also be descriptively summarized by each timepoint.

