9.5. Electrocardiogram

Triplicate ECG recordings will be obtained at each scheduled timepoint and the average of the three readings will be used to determine ECG intervals, including QRS, heart rate, PR, QT, Corrected QT interval using Fridericia's formula (QTcF), Corrected QT interval using Bazett's formula (QTcB) and RR. Missing ECG data will not be imputed. If one or two replicates are missing, the average will be calculated on the available replicates.

ECG Numeric Variables

HR, PR, QRS, QT, QTcF, QTcB, and RR will be summarized using descriptive statistics. The change from baseline of these ECG parameters at each timepoint will be listed for each subject. For each timepoint of measurement, the changes from baseline will be summarized using descriptive statistics.

Categorical Analysis

The cumulative incidence count and percentage of subjects with any postdose QTcF values of > 450 msec, > 480 msec, and > 500 msec will be tabulated for all subjects. Subjects will be listed with corresponding baseline values, Δ QTcF, and baseline and treatment HR. The cumulative incidence count and percentage of subjects with Δ QTcF increase of > 30 msec and > 60 msec will be tabulated. Also subjects with QTcB/QTcF >480 ms and/or change from baseline in QTcB/QTcF >60 ms will also be listed in a separate listing.

Morphology Findings

New ECG morphologies for each subject not present on any ECG at baseline for that subject will be summarized for all observation timepoints combined.

The number and percentage of subjects having new morphology changes from baseline will be reported, and summarized as QTc Prolongation, ST depression, ST elevation, T-waves biphasic, T-waves flat, T-wave inversion, or U-wave abnormality.

ECG overall interpretation by visit will be presented in a listing.

For the schedule of ECG test, please refer to Appendix 1.

10. Pharmacokinetics

Blood samples for plasma PK analysis of MYK-461 will be collected within 2 hours prior to dosing at the following timepoints: Day 1, Week 1, Week 2, Week 3, Week 4, Week 5, Week 6, Week 7, Week 8, Week12 and Week 16 or End of Study (End of Treatment + 4 Week) for Part A and Part B.

Concentrations that are BLQ will be treated as zero for descriptive statistics. All missing concentrations will be treated as missing for descriptive statistics.

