APPENDIX 1 SCHEDULE OF STUDY PROCEDURES

Timepoint (Day/Week) ^a	Screen D -28 to D -1	D1	W1	W2	W3	W4	W5	W6	W7	W8	W12/ ET	W16/ EOS or ET + 4W
General Procedures												
Informed consent	X											
Medical history ^b	X											
Telephone call to subject ^c		←→								←→		
Vital signs ^d	X	X	X	X	X	X	X	X	X	X	X	X
AEs/SAEs ^e	X	X	X	X	X	X	X	X	X	X	X	X
Concomitant therapy	X	X	X	X	X	X	X	X	X	X	X	X
Physical examination ^f	X	X	X	X	X	X	X	X	X	X	X	X
Body height	X											
Body weight	X	X									X	X
ECG ^g	X	X	X	X	X	X	X	X	X	X	X	X
Resting TTE ^h	X	X	X	X	X	X	X	X	X	X	X	X
CPET ⁱ		X									X ^j	
Hemodynamic stress echocardiography ^k	X					X					X	X
Optional pulse wave optical biosensor ^l	X	X	X	X		X				X	X	X
Apply cardiac monitoring skin patch ^m	X	X		X		X		X		X ⁿ	X	
Retrieve previously applied cardiac monitoring skin patch ^m		X		X		X		X		X	X	X
Laboratory												
Hepatitis panel, HIV test, TSH, and drug/alcohol testing	X											
PK samples ^o		X	X	X	X	X	X	X	X	X	X	X
Chemistry	X	X				X				X	X	X
Hematology	X	X				X				X	X	X
Urinalysis	X	X									X	X

Footnotes and abbreviations defined on last page of table.

- ^d Vital signs include temperature, HR, respiratory rate, and BP after resting for at least 5 minutes. Obtain vital signs with subject in the same position; BP and HR should be the mean of 3 measurements taken ≥ 5 min apart. BP should be taken via an automated recorder. On Day 1, vital signs will be taken predose and at 1 hour postdose. At all other visits, vital signs will be taken predose.
- ^e Any changes in baseline conditions that occur after the ICF is signed are recorded on the medical history eCRF, unless the change is related to a study procedure, in which case it is considered an AE. All changes that occur after the administration of the study medication are recorded as AEs.
- ^f At Screening, Day 1, Week 12, and Week 16, a complete physical examination will be conducted including a neurological examination (gross motor and deep tendon reflexes), height (Screening only) and weight, and assessment of the following: general appearance, skin, head and neck, mouth, lymph nodes, thyroid, abdomen, musculoskeletal, cardiovascular, neurological, and respiratory systems. At all other visits, an abbreviated cardiopulmonary physical examination will be conducted, with other systems assessed as directed by interval history.

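### SAP visit windows count only days since first dose, so after a stop on Day 51–71 the four-week washout echo can enter the primary model as Week 12 (end of treatment)

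*SAP*

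**What the plan says.** **Windows.** SAP Section 4 (General Statistical Considerations) says that the "analysis visit window for weekly visits will consider +/- 3 days of the scheduled visit date based on the date of first exposure" to study drug, with first dose as Day 1. The sentence speaks of weekly visits, but its table also covers Week 12 (Days 79–99, target Day 85) and Week 16 (Days 100–116, target Day 113). The reason given is that a missed evaluation is rescheduled, "thus analysis windows have been designed to be all-inclusive". There is no row for ET, no use of the last dose date, and no statement that the scheduled visit label overrides the study day. The section's one remark on early discontinuation concerns stops before Week 4, and only which table columns those subjects appear in.

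**Schedule.** SAP Appendix 1 places stress echocardiography in the W12/ET column and again in the column headed "W16/ EOS or ET + 4W". SAP Section 10 likewise describes the last PK sample as "Week 16 or End of Study (End of Treatment + 4 Week". Among the options in Protocol 5.5.1 is "Withdraw from treatment and agree to participate in the Early Termination and End of Study (EOS) visits".

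**Model and population.** The primary MMRM in SAP 8.1 takes all available data and has "fixed categorical effects of timepoint: baseline, Week 4, Week 12 (end of treatment), and Week 16 (EOS") as its only timepoints. The Efficacy Analysis Population (SAP 4.3.2) keeps dosed subjects who "have primary or secondary endpoint data, including a baseline value and at least one post baseline value". Protocol 5.5.2 lets the sponsor replace some dropouts, but "All data from subjects who receive at least 1 dose of IMP will be documented and maintained in the clinical trial database".

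**The concern.** The window table and the schedule label the same two visits differently. The schedule treats the ET echo as the Week 12 assessment and the echo four weeks later as the Week 16 washout assessment. The study-day table knows nothing of when treatment stopped. For a band of stopping days it files the washout echo under Week 12 and puts the ET echo in a week that the primary model does not use.

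The primary contrast is baseline against Week 12, which the model calls end of treatment. A value taken four weeks off drug does not fit that name. If the gradient has returned toward baseline by then, the estimated reduction is too small. With about 10 subjects per part, one such subject is a tenth of the sample. The Week 12 responder summaries, and the Week 12 values of the other endpoints collected at these visits, would carry the same label.

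**Working it through.** **1. Which stopping days are affected.** Inputs from the SAP Section 4 table: Week 7 = 47–53, Week 8 = 54–64, Week 10 = 65–78, Week 12 = 79–99, Week 16 = 100–116. The follow-up visit is at ET + 28 days (SAP Appendix 1). The last dose is taken to be at about the ET visit.

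- The follow-up falls in Week 12 when 79 ≤ ET + 28 ≤ 99, so ET runs from 79 − 28 = 51 to 99 − 28 = 71. That is 21 days.
- If the follow-up is a day early or late, the range is Day 52–72 or Day 50–70.
- A stop at the scheduled Week 8 visit (Day 57) gives 57 + 28 = 85, the Week 12 target day.

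| ET day | Label of ET echo | Label of ET + 28 echo |
|---|---|---|
| 1–4 | Day 1 | Week 4 |
| 5–50 | Weeks 1–7 | Weeks 5–10 (not model timepoints) |
| 51–53 | Week 7 | Week 12 |
| 54–64 | Week 8 | Week 12 |
| 65–71 | Week 10 | Week 12 |
| 72–85 | Week 10 or 12 | Week 16 |

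For Days 51–71 the ET echo does not compete for the Week 12 slot, so the closest-to-target and tie rules never come into play, and Week 16 is empty.

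**2. The plan's own power figure.** SAP 4.1 gives n = 10, SD 35 mm Hg and one-sided 5%. The standard error is 35/√10 = 11.07. A paired t-test on 9 degrees of freedom gives power of 51%, 80%, 95% and 99.4% for changes of 20, 30, 40 and 50 mm Hg. This reproduces the SAP's 50, 80, 95 and >99.

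**3. Size of the shift.** The documents give no dropout rate and no washout data in these patients, so the number affected (k) and the fraction of the effect reversed (r) are assumptions. Some reversal is plausible: with the half-life of about 8 days in Protocol 1.2.1 (single dose, healthy men), 0.5^(28/8) = 9% of drug remains at 28 days. When an affected subject lacks only Week 16, the MMRM point estimate at Week 12 equals the plain paired mean, so

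expected estimate = 30 × (1 − k·r/10).

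| k | r | Estimate (mm Hg) | Bias / 11.07 | Power (simulated) |
|---|---|---|---|---|
| 0 | – | 30.0 | 0 | 80% |
| 1 | 0.5 | 28.5 | 1.5/11.07 = 0.14 | 76% |
| 1 | 1 | 27.0 | 3.0/11.07 = 0.27 | 71% |
| 2 | 0.5 | 27.0 | 0.27 | 72% |
| 2 | 1 | 24.0 | 6.0/11.07 = 0.54 | 60% |

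For a true change of 50 and k = 1 the estimates are 47.5 and 45.0. If the dropout is replaced (n = 11, k = 1), the estimate is 30 × (1 − r/11) = 28.6 or 27.3.

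**4. Comparators for one affected subject.** Leaving Week 12 missing (n = 9) gives 76% power. Using the schedule's labels gives 80%, if the ET echo shows the full effect (assumption). In an MMRM simulation with an assumed correlation of 0.5, the root mean squared error is 11.2–11.5 under the windows, about 11.7 with Week 12 missing, and 11.1 with schedule labels.

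**The case against.** The strongest reply is that the harmful reading is not the intended one. The window sentence speaks of weekly visits and justifies itself by rescheduled evaluations, and an ET or post-ET visit is neither. The schedule, the PK section and the model's own timepoint names all suggest ET as Week 12 and the later visit as Week 16. An analyst might well use those labels. This stands as far as it goes: a reader might infer that the washout echo *will* be used as Week 12, and the documents support only that it *can* be. But the only written assignment rule points the other way, and two competent programmers could build different primary datasets.

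Other stronger readings also fail:

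- *The primary result could be falsely positive.* If there is no effect there is nothing to reverse; a return toward baseline only shrinks the estimate.
- *The Week 12 to Week 16 reversibility endpoint is necessarily distorted.* That holds only if the contrast is taken from the MMRM. SAP 8.2 does not list this endpoint for the MMRM, and Table 14.2.1.3 carries no MMRM tag. If the change is summarised in subjects with both values, the affected subject simply drops out.
- *The Day 65–99 window widens the problem.* Applied to echoes, it would extend the affected range to Day 37–71, but the footnote introduces that window for CPET.

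It is also fair to say that the case is narrow (a stop within one 21-day span, with the off-drug stress echo attended), and that an off-drug value at calendar Week 12 is legitimate under a treatment-policy aim. The SAP states no such aim, and its end-of-treatment label does not suit one.

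**Conclusion.** The point holds as a labelling fault in the SAP. The written windows conflict with the SAP's own schedule for stops on Day 51–71, and no text settles which prevails. The day range is exact arithmetic, given a follow-up 28 days after ET.

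The size is conditional. With one of 10 subjects affected and half to full reversal, the loss is 1.5 to 3.0 mm Hg on a true 30, always toward zero. Compared with leaving Week 12 missing, the windows cost no power at half reversal and about 5 points at full reversal, and their total error is slightly lower. The case for change is therefore a correct label and an unambiguous primary dataset rather than a large gain in precision. Severity is minor.

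**What to change.** In SAP Section 4:

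1. State that, for subjects who stop treatment early, the visit four weeks after ET keeps its scheduled Week 16/EOS (washout) label and is never assigned to Week 4 or Week 12 by study day. List actual days on and off drug for these subjects.
2. State in advance whether the ET echo enters the primary model under its scheduled W12/ET label or is left out, and run the other choice as a sensitivity analysis.
3. If a treatment-policy value at calendar Week 12 is what is wanted, say so and drop the end-of-treatment label.

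The cost is two or three sentences and one programming rule. Each choice for the ET echo has a downside. Leaving it out means an occasional missing Week 12 value, handled under a missing-at-random assumption that is doubtful when withdrawal is for adverse events. Keeping the schedule label means that an early stopper's echo counts as Week 12 after short exposure. The listing and the sensitivity analysis would show either effect.
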